5.6. Other Considerations for Data Analyses and Data Handling Conventions

Other considerations for data analyses and data handling conventions are outlined in the appendices:

Section	Component
Section 13.2	Appendix 2: Schedule of Activities
Section 13.3	Appendix 3: Assessment Windows
Section 13.4	Appendix 4: Study Phases and Treatment State
Section 13.5	Appendix 5: Data Display Standards & Handling Conventions
Section 13.6	Appendix 6: Derived and Transformed Data
Section 13.7	Appendix 7: Reporting Standards for Missing Data
Section 13.8	Appendix 8: Values of Potential Clinical Importance
Section 13.9	Appendix 9: Population Pharmacokinetic (PopPK) Analyses
Section 13.10	Appendix 10: Pharmacokinetic / Pharmacodynamic Analyses
Section 13.11	Appendix 11: Snapshot Algorithm Details
Section 13.14	Appendix 14: IDMC
Section 13.15	Appendix 15: Variables Defined for Time to Event Analysis
Section 13.16	Appendix 16: Example Mock Shells for Data Displays

6. STUDY POPULATION ANALYSES

6.1. Overview of Planned Study Population Analyses

The study population analyses will be based on the Intent-to-Treat Exposed population, unless otherwise specified.

Study population analyses including analyses of subject's disposition, protocol deviations, demographic and baseline characteristics, prior and concomitant medications, and exposure and treatment compliance will be based on GSK Core Data Standards. Details of the planned displays are presented in [Appendix 13: List of Data Displays](#).

[Table 2](#) provides an overview of the planned study population analyses, with full details of data displays being presented in [Section 13.13: List of Data Displays](#).

Table 2 Overview of Planned Study Population Analyses

Display Type	Data Displays Generated	
	Table	Listing
Randomisation		
Randomisation ^[1]		Y ^[2]
Subject Disposition		
Study Populations ^[3]	Y	Y ^[4]
Study Recruitment ^[3]	Y	Y
Reasons for Screening Failures ^[3]	Y	Y
History of Rescreened Subjects ^[3]		Y
Age categories	Y	
Subject Disposition	Y ^{[5][6]}	
Reasons for Withdrawal by Visit	Y ^{[5][6]}	Y
IP discontinuation	Y	Y
Important Protocol Deviations	Y	Y
Deviations leading to exclusion from PP	Y	Y
Inclusion and Exclusion Criteria Deviations	Y	Y
Demography and Baseline		
Demographics Characteristics ^[7]	Y	Y
Race & Racial Combinations ^[8]	Y	Y
Hepatitis Status	Y	Y
CDC Classification of HIV infection (2014)	Y	Y
Cardiovascular Risk Assessments at Baseline	Y	Y
Distribution of CD4+ Cell Counts	Y	
History of Cardiac Therapeutic Procedures		Y

Display Type	Data Displays Generated	
	Table	Listing
Medical Conditions, Concomitant Medications & Antiretroviral Therapy		
Medical Conditions (Current/Past) ^[9]	Y	Y
Medical Conditions: Sub-conditions (Current/Past) ^[9, 10]	Y	
Concomitant Medications (non-ART)	Y ^[11]	Y ^[12]
Antiretroviral Therapy stopped Prior to Screening ^[13]	Y	Y ^[14]
Antiretroviral Therapy Taken during Screening	Y	Y ^[15]
Antiretroviral Therapy Taken Prior to & during Screening for Subjects Failing ART Eligibility Criteria		Y
Concomitant Antiretroviral Therapy at Maintenance Phase	Y	Y ^[15]
Baseline third agent class (Strata) ^[16]	Y	Y
Lipid Modifying agents (Baseline and Post-Baseline)	Y	
Substance use	Y	Y
Other		
Study Treatment Accountability ^[17]		Y

NOTES:

- T = Tables, L = Listings, Y = Display Generated,
1. All Participants Randomized population
 2. One listing of subjects randomized but not treated, and one listing of planned and actual treatment strata.
 3. All Subjects screened population.
 4. Listing will be based on all subjects screened population
 5. Subjects who have not been recorded as either completing or withdrawing from the study will be categorized as "Ongoing at time of the analysis" for summary purposes.
 6. Analysis of subject disposition will be performed for each study phase separately, as well as for overall study conclusion.
 7. Age and ethnicity collected at Screening; weight and height collected at Day 1
 8. The five high-level FDA race categories and designated Asian subcategories will be summarised along with all combinations of high-level categories which exist in the data. The nine race categories collected will be summarised along with categories for mixed race. A by-subject listing of race will also be produced.
 9. Medical conditions will be coded using the Medical Dictionary for Regulatory Activities (MedDRA).
 10. Sub conditions are Cardiac, Gastrointestinal, Metabolism and Nutrition, Psychiatric, Renal and Urinary, and Nervous System Conditions
 11. Three separate tables, summarised by Ingredient ATC Level 1, Ingredient combinations and Combination term ATC Level 1 (EG Includes single-ingredient medications with multi-ingredient medications labeled according to the sum of their ingredients, e.g., "TYLENOL Cold and Flu" would appear as "CHLORPHENAMINE MALEATE + DEXTROMETHORPHAN HYDROBROMIDE + PARACETAMOL + PSEUDOEPHEDRINE HYDROCHLORIDE" under the ATC headings for "Nervous System" and "Respiratory System" (the combination's ATC classifications).)
 12. One listing for concomitant non-ART medications and one listing showing the relationship between verbatim text, ingredient and ATC Level 1.
 13. Include medications that started and stopped prior to 6 months before screening
 14. One listing for Prior ART stopped prior to Screening and one listing showing the relationship between verbatim text, ingredient, combination and ATC Level 4 for all ART.
 15. Separate Listing of for ART taking during Screening and taken concomitant ARTs
 16. Based on the actual third agent class derived from the eCRF CONART data collection of what the subjects actually took, regardless of the strata they were randomized into.
 17. Dispensation information (dates and number of tablets dispensed and returned).

7. EFFICACY ANALYSES

7.1. Primary Efficacy Analyses

7.1.1. Endpoint / Variables

Where applicable, describe the method for combining measurements to create composite variables. Flexibility to include this information in Proportion of participants with plasma HIV-RNA greater than or equal to 50 copies/mL as per Food and Drug Administration (FDA) Snapshot algorithm at Week 48 (Intent-to-Treat Exposed [ITT-E] population); see Section 13.11 for additional details. [Appendix 6](#): Derived and Transformed Data.

7.1.2. Summary Measure

Difference in the proportion of participants with HIV-RNA ≥ 50 c/mL at Week 48 (defined by the US FDA snapshot algorithm) between each treatment group (Q4W IM – Current ART).

7.1.3. Population of Interest

The primary efficacy analyses will be based on the Intent-To-Treat Exposed population, unless otherwise specified.

7.1.4. Strategy for Intercurrent (Post-Randomization) Events

As defined by the Snapshot algorithm, HIV-RNA ≥ 50 copies/mL is determined by the last available HIV-1 RNA measurement while the participant is on treatment within the analysis visit window of interest.

Participants without evaluable HIV-RNA data for the visit of interest and who discontinue treatment for reasons not related to adverse event while having HIV-1 RNA ≥ 50 copies/mL at time of discontinuation or who change study treatment not permitted per protocol before the analysis window are classified as having HIV-RNA ≥ 50 copies/mL.

7.1.5. Statistical Analyses / Methods

[Table 3](#) provides an overview of the planned efficacy analyses. Details of the planned displays are provided in [Appendix 13](#): List of Data Displays and will be based on GSK data standards and statistical principles.

Table 3 Overview of Planned Primary Efficacy Analyses

Endpoints	Stats Analysis			Summary		Individual	
	T	F	L	T	F	F	L
Proportion of Subjects with 'HIV-1 \geq 50 c/mL' at Week 48 – Snapshot							
Primary analysis of comparison between the two groups (CAB – current ART) in 'HIV-1 RNA \geq 50' rates at Week 48	Y ^[1]			Y ^[1,2]	Y ^[4]		Y ^[2]
Treatment Heterogeneity across randomization strata	Y						
By Subgroup ^[3] (Exploratory analysis to support primary analysis)				Y ^[5]	Y ^[4]		

NOTES:

- T = Table, F = Figure, L = Listing, Y = Yes display generated.
 - Stats Analysis = Represents TFL related to any formal statistical analyses (i.e. modelling) conducted.
 - Summary = Represents TFL related to any summaries (i.e. descriptive statistics) of the observed raw data.
 - Individual = Represents FL related to any displays of individual subject observed raw data.
1. Generated using the 'Intent-to-Treat Exposed' (primary) and 'Per-Protocol' (sensitivity) populations.
 2. Study outcomes (i.e., response below 50 c/mL, 'HIV-1 RNA \geq 50' or reason for no data in the window) based on the snapshot algorithm.
 3. Randomisation Strata, demographic and Baseline Characteristics (refer to Section 5.4).
 4. Plot of the difference in proportion of subjects \geq 50 c/mL (Snapshot algorithm) and its 95% confidence intervals for 'overall' (on the top of the figure) and by subgroup at Week 48.
 5. Study outcomes based on the Snapshot algorithm by subgroup at Week 48 will also be produced.

7.1.5.1. Statistical Methodology Specification

Primary Statistical Analyses
Endpoint

 Proportion of Participants with Plasma HIV-1 ≥ 50 c/mL at Week 48 using the Snapshot algorithm for the ITT-E population. ‘HIV-1 RNA≥ 50’ are based on the Snapshot algorithm includes subjects who had plasma HIV-1 RNA ≥ 50 c/mL at Week 48, who discontinued for lack of efficacy, who discontinued for other reasons while not < 50 c/mL, or who changed ART).
Snapshot Dataset

 Virologic outcome (‘HIV-RNA < 50’ or ‘≥ 50 copies/mL’) per Snapshot algorithm is determined by the last available on-treatment HIV-1 RNA measurement within the analysis visit window of interest (please refer to analysis window defined in Table 11). In addition, subjects who discontinue for reasons not related to adverse event with on-treatment HIV-1 RNA result at the time of discontinuation ≥ 50 copies/mL or who change study treatment not permitted per protocol during maintenance phase before the analysis visit are classified as ‘HIV-RNA ≥ 50 copies/mL’. Full details of the Snapshot algorithm are provided in Section 13.11.
Model Specification

 The primary efficacy endpoint will be analysed using a stratified analysis with Cochran-Mantel-Haenszel (CMH) weights, adjusting Baseline third agent class (PI, INI, or NNRTI) and sex at birth The CMH estimate of the adjusted treatment difference will be calculated as a weighted average of strata-specific estimates of the treatment difference calculated within each of the following Baseline analysis strata resulting from the cross classification of both stratification factors: 
 Baseline third agent class PI AND Male sex at birth Baseline third agent class PI AND Female sex at birth Baseline third agent class INI AND Male sex at birth Baseline third agent class INI AND Female sex at birth Baseline third agent class NNRTI AND Male sex at birth Baseline third agent class NNRTI AND Female sex at birth If n_k is the number of CAB LA + RPV LA treated subjects, m_k is the number of the control arm treated subjects, and $N_k = n_k + m_k$ is the total number of subjects in the kth stratum, then the CMH estimate is given by $\hat{d}_{cmh} = \frac{\sum W_k \hat{d}_k}{\sum W_k}$ 
where

Primary Statistical Analyses

$$W_k = \frac{n_k m_k}{N_k}$$

are CMH weights and \hat{d}_k are estimates of the differences in proportions between the two treatment arms, $f_{Q8W}-f_{Q4W}$, for the k th stratum.

- The corresponding two-sided 95% CI will be calculated as

$$\hat{d}_{cmh} \pm 1.96 \times \sqrt{\hat{\text{var}}(\hat{d}_{cmh})}$$

where the variance estimator [Sato, 1989] is consistent in both sparse data and large strata and is given below

$$\hat{\text{var}}(\hat{d}_{cmh}) = \frac{\hat{d}_{cmh} (\sum P_k) + \sum Q_k}{(\sum n_k m_k / N_k)^2} = \frac{\hat{d}_{cmh} (\sum P_k) + \sum Q_k}{(\sum W_k)^2}$$

where

$$P_k = \frac{n_k^2 y_k - m_k^2 x_k + n_k m_k (m_k - n_k) / 2}{N_k^2}$$

$$Q_k = \frac{x_k (m_k - y_k) / N_k + y_k (n_k - x_k) / N_k}{2}$$

with x_k and y_k corresponding to the number of participants with Plasma HIV-1 ≥ 50 c/mL at Week 48 per FDA Snapshot for CAB LA + RPV LA and Current ART, respectively, for the k th stratum.

Model Results Presentation

- Adjusted CMH estimate of the difference in the proportion of subjects with ‘HIV-1 RNA ≥ 50 ’ between each treatment group (CAB LA + RPV LA – Current ART) and corresponding 95% confidence interval.
- Non-inferiority will be concluded if the upper bound of the two-sided 95% confidence interval (CI) for the CMH adjusted difference in proportion of subjects with ‘HIV-1 RNA ≥ 50 ’ in the CAB LA + RPV LA group minus proportion of subjects with ‘HIV-1 RNA ≥ 50 ’ in the Current ART group is less than 6%.
- If the analysis shows non-inferiority then a superiority hypothesis will be tested at the two-sided 5% level of significance. Superiority favoring CAB LA + RPV LA will be declared if the upper end of the confidence interval is below 0% for the ITT-E population analysis. If superiority is declared, the p-value for superiority will also be calculated.

Primary Statistical Analyses
Subgroup Analyses

 1. Treatment Heterogeneity across randomization strata: 
 • The weighted least squares chi-squared statistic [Fleiss, 1981] will be used to test for one-way homogeneity across the levels of each categorical variable, with each categorical variable considered separately. • Following Lui and Kelly [Lui, 2000] $\frac{1}{2}$ will be added to each cell in any strata for which the stratum-specific rate estimates of either r_d or r_a are zero or one, and tests will be one-sided. • Any heterogeneity found to be statistically significant will be explored and if necessary results will be reported for each level of the categorical variable. Investigation of heterogeneity will be confined to the primary. Tests of homogeneity will be assessed at the one-sided 10% level of significance. 2. Exploration of Subgroup 
 • An analysis for subgroups listed in Section 5.4.2 will be performed. This will show the proportion of subjects with plasma HIV-1 RNA ≥ 50 c/mL at the time of analysis (Week 48) based on the Snapshot algorithm and will be presented by treatment group. • Unadjusted difference in proportions between treatment groups and corresponding two-sided 95% CI will also be presented by subgroups. These results will also be presented graphically. 3. Summary of study outcomes (i.e., response below 50 c/mL, 'HIV-1 RNA≥ 50' or reason for no data in the window) by subgroup will be produced. 4. Note: These subgroup analyses will be exploratory and likely underpowered so that interpretation may therefore focus on point estimates as well as the upper bounds of 95% CIs for the treatment differences and response rates. Additionally, multiple comparisons are being made which inflates the risk of false positive findings. Therefore, if consistent findings across the multiple comparisons were observed then these analyses would still be suggestive of a generalizable finding of non-inferiority.
Sensitivity and Supportive Analyses

 1. Per-protocol population analysis: 
To assess the impact of important protocol deviations, statistical analysis will be repeated using the Per-protocol population and compared for consistency with the results from the primary ITT-E population analysis.

7.2. Secondary Efficacy Analyses

7.2.1. Endpoint / Variables

Proportion of participants with plasma HIV-1 RNA < 50 c/mL (c/mL) at Week 48 using the FDA Snapshot algorithm (Intent-to-Treat Exposed [ITT-E] population).

7.2.2. Summary Measure

Difference in the proportion of participants with HIV-RNA < 50 c/mL at Week 48 (defined by the US FDA snapshot algorithm) between each treatment group (Q4W IM – Current ART).

7.2.3. Population of Interest

The secondary efficacy analyses will be based on the Intent-to-Treat Exposed population, unless otherwise specified.

7.2.4. Strategy for Intercurrent (Post-Randomization) Events

Participants with last available HIV-1 RNA measurement less than 50 copies/mL while the participant is on treatment within the analysis visit window of interest are classified as responders.

Participants without evaluable HIV-RNA data for the visit of interest or who change treatment not permitted per protocol before the analysis window are considered non-responders.

7.2.5. Statistical Analyses / Methods

Details of the planned displays are provided in [Appendix 13: List of Data Displays](#) and will be based on GSK data standards and statistical principles.

[Table 4](#) provides an overview of the planned efficacy analyses. Details of the planned displays are provided in [Appendix 13: List of Data Displays](#) and will be based on GSK data standards and statistical principles.

Table 4 Overview of Planned Secondary Efficacy Analyses

Endpoints	Stats Analysis			Summary		Individual	
	T	F	L	T	F	F	L
Proportion of Participants with Plasma HIV-1 < 50 c/mL at Week 48 – Snapshot^[1]							
Key secondary analysis	Y ^[2]			Y ^[2, 3]	Y		Y ^[3]
Treatment Heterogeneity across randomization strata	Y						
Proportion of Participants without efficacy-related discontinuation (ERDF) or treatment-related discontinuation (TRDF) failure (refer to Section 13.6.4)							
Kaplan-Meier estimate				Y			
Proportion of Subjects with Plasma HIV-1 RNA ≥50 copies/mL over time through Week 48– Snapshot							
by Visit				Y	Y ^[4]		
by Visit and Subgroup ^[5]				Y	Y		

Endpoints	Stats Analysis			Summary		Individual	
	T	F	L	T	F	F	L
Proportion of Subjects with Plasma HIV-1 RNA <50 copies/mL over time through Week 48– Snapshot							
by Visit				Y	Y ^[6]		
by Visit and Subgroup ^[5]				Y	Y ^[7]		
Proportion of Subjects with Plasma HIV-1 RNA <200 copies/mL over time through Week 48– Snapshot (also for ≥200 copies/mL)							
by Visit				Y ^[8]	Y ^[9]		
Proportion of Subjects with Plasma HIV-1 RNA <50 copies/mL at Week 48 by delay in IP injection^[10] - Snapshot (exploratory analysis)							
by Delay in IP injection				Y			Y
Proportion of Subjects with Plasma HIV-1 RNA <2 copies/mL (exploratory analysis)							
by Visit - Observed Case Analysis				Y			Y

1. This analysis will be performed using the similar approach as described for the primary analysis in Section 7.1.5.1
2. Generated using the 'Intent-to-Treat Exposed' (primary) and 'Per-Protocol' (sensitivity) populations.
3. Study outcomes (i.e., response below 50 c/mL, 'HIV-1 RNA≥50' or reason for no data in the window) based on the snapshot algorithm.
4. Line plots, with 95% confidence intervals(CIs), for the proportion of subjects HIV-1 RNA ≥50c/mL for overall and by treatment group at each visit. The 95% CIs will be calculated using Exact (Clopper-Pearson) confidence interval if the proportion is 0%. Otherwise, they are derived using the normal approximation.
5. Randomisation strata, Baseline and demographic factors (refer to Section.5.4)
6. Line plots, with 95% confidence intervals, for the proportion of subjects <50c/mL by treatment group at each visit.
7. Plot of the difference in proportion of subjects <50 c/mL and its 95% confidence intervals (Snapshot algorithm) by subgroup for Week 48 only.
8. Study outcomes (i.e., HIV-1 RNA< 200 c/mL, HIV-1 RNA≥200c/mL, or reason for no data in the window) based on the snapshot algorithm by subgroup for Week 48 will also be produced.
9. Line plots, with 95% confidence intervals, for the proportion of subjects <200c/mL and ≥200 c/mL by treatment group at each visit.
10. Delay in IP injection (days) is defined in Section 13.6.4

Endpoints	Absolute						Change from Baseline							
	Stats Analysis			Summary		Individual		Stats Analysis			Summary		Individual	
	T	F	L	T	F	F	L	T	F	L	T	F	F	L
Plasma HIV-1 RNA Over Time														
Observed ^[1]				Y		Y ^[2]	Y ^[3]							
Detected vs Non-detected by Visit ^[5]				Y			Y ^[6]							
Confirmed Virologic Failure (CVF)														
CVF by Visit				Y			Y							
HIV-1 RNA at time of suspected and confirmed Virologic Failure				Y										
CD4+ , CD8+ Cell Counts Over Time														
CD4+ Observed				Y							Y			Y
CD8+ observed				Y							Y			Y
CD4+/CD8+ ratio observed				Y										
Post-baseline HIV-1 Conditions and Disease Progression														
HIV Conditions including/excluding Recurrences as recorded in eCRF				Y			Y							
HIV Disease Progressions ^[4]				Y										

NOTES:

- T = Table, F = Figures, L = Listings, Y = Yes display generated
 - Stats Analysis = Represents TFL related to any formal statistical analyses (i.e. modelling) conducted.
 - Summary = Represents TFL related to any summaries (i.e. descriptive statistics) of the observed raw data.
 - Individual = Represents FL related to any displays of individual subject observed raw data.
1. Using observed case (OC) data which contains the data that is available at a particular time point, with no imputation for missing values.
 2. Individual plasma HIV-1 RNA only for subjects who are in the category of ‘viral load ≥ 50 c/mL’ at Week 48 per Snapshot algorithm or who are CVF subjects. The figures will display all HIV-1 RNA values observed.
 3. Include the interpretation of whether the virus is detected or not (‘Detected’ or ‘Not detected’) by the assay.
 4. HIV disease progressions (Section 13.6.4)
 5. See Section 13.6.4 for a definition of “Target Detected” and “Target Non-detected”.
 6. Included in the Observed HIV-1 RNA listing

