2.3. Study Design

Overview of Study Design and Key Features	

The diagram illustrates the study design timeline. It is divided into three main phases: Screening Phase, Maintenance Phase, and Extension Phase. The Screening Phase (Day 1) involves randomization (1:1, N=570) into two arms: 'PI, NNRTI or INI Based Regimen with 2 NRTI Backbone' and 'Oral CAB + RPV'. The Maintenance Phase (Day 1 to Week 52) continues with 'PI, NNRTI or INI Current ART' for the first arm and 'CAB LA + RPV LA' for the second. At Week 52, the first arm has an optional 'Extension Phase' (Oral CAB + RPV), while the second arm enters an 'Extension Phase'. Both arms have a '1° Endpoint' at Week 48 and a '2° Endpoint' at Week 96. 'Q4 Weeks' intervals are marked between Week 48 and Week 52, and between Week 56 and Week 96.
	

N=570, randomized 1:1 to each arm and stratified by baseline 3rd Agent class and sex at birth. # Must be on uninterrupted current regimen (either the initial or second cART regimen) for at least 6 months prior to Screening. Documented evidence of at least two plasma HIV-1 RNA measurements <50 c/mL in the 12 months prior to Screening: one within the 6 to 12 month window, and one within 6 months prior to Screening. No history of virologic failure. No evidence of viral resistance based on the presence of any resistance-associated major INI, or NNRTI mutation (except K103N) from prior genotype assay results. No current or prior history of etravirine use. ΨINI based regimen excludes abacavir/dolutegravir/lamivudine (TRIUMEQ), and INI therapy will be capped at approximately 40% of study enrolment for current ART †Optional Extension Phase to CAB LA + RPV LA at Wk 52 for participants randomized to current ART ‡Participants who withdraw from IM arm must go into 52 week long term follow up phase
	

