13.6.4. Efficacy

Snapshot

 The Snapshot algorithm is intended to be primarily a virologic assessment of the endpoint, and as such follows a “virology first” hierarchy. ‘HIV-1 RNA <50 c/mL’ or ‘HIV-1 RNA ≥50 c/mL’ within an analysis window (see Table 11) is typically determined by the last available HIV-1 RNA measurement in that window while the subject is On-treatment in the Maintenance Phase (as assigned based on Table 20). 
 When no HIV-1 RNA data is available within a window, a subject cannot be assigned to the category of ‘HIV-1 RNA < 50 c/mL’. Depending on the reason for lack of data, the subject will be classified as a ‘HIV-1 RNA≥50’ or reported as ‘No Virologic Data at Week X’; in the latter case, the algorithm further classifies the nature of the missing data. Typically, a subject withdrawn (i) due to AE or, (ii) for another reason yet was suppressed at the time, will be counted as ‘No Virologic Data at Week X’. Should a subject withdraw for reasons other than AE and was not suppressed at the time, they will be a ‘HIV-1 RNA≥50’. For each scheduled assessment time, the Snapshot response rate for a given threshold (e.g., <50 c/mL) is defined as: $\text{Snapshot Response Rate} = \frac{\text{Number of responders in that analysis window}}{\text{Number of subjects in the analysis population}}$ 
 For each scheduled assessment time, the Snapshot ‘HIV-1 RNA≥50’ rate for a given threshold (e.g., ≥50 c/mL) is defined as: $\text{Snapshot VF Rate} = \frac{\text{Number of VFs in that analysis window}}{\text{Number of subjects in the analysis population}}$ 
 Full details of the algorithm, including the handling of special cases, are included in Section 13.11
Plasma HIV-1 RNA

 For summaries and analyses which use HIV-1 RNA level as a continuous measure, the logarithm to base 10 of the value will be used. HIV-1 RNA results may be provided as censored values, such as <40 or >9,999,999 c/mL. For the purposes of summary statistics, such values will be replaced by the next value beyond the limit of detection, e.g., 39 or 10,000,000 c/mL, respectively, for the given examples. Data listings will show the censored values as provided.
Target Detected / Target Non-Detected/Super low viral load testing

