13.13.6. Efficacy Figures

Efficacy: Figures					
No.	Population	IDSL / TST ID / Example Shell	Title	Programming Notes	Deliverable [Priority]
Primary Efficacy Analyses					
2.1.	ITT - E	Shell FPEF1	Proportion (95% CI) of Subjects with HIV-1 RNA ≥ 50 c/mL by Visit – Snapshot Analysis		HL, WK48
2.2.	ITT - E	Shell FPEF2	Unadjusted Treatment Difference in Proportion (95% CI) of Subjects with HIV-1 RNA ≥ 50 c/mL at Week 48 by Subgroup – Snapshot Analysis		WK48
Secondary Efficacy Analyses					
2.3.	ITT - E	Shell FPEF1	Proportion (95% CI) of Subjects with HIV-1 RNA < 50 c/mL by Visit – Snapshot Analysis		HL, WK48
2.4.	ITT - E	Shell FPEF2	Unadjusted Treatment Difference in Proportion (95% CI) of Subjects with HIV-1 RNA < 50 c/mL at Week 48 by Subgroup – Snapshot Analysis		WK48

Efficacy: Figures					
No.	Population	IDSL / TST ID / Example Shell	Title	Programming Notes	Deliverable [Priority]
2.5.	ITT - E	Shell FPEF1	Proportion (95% CI) of Subjects with HIV-1 RNA <200 c/mL by Visit – Snapshot Analysis		WK48
2.6.	ITT-E	Mid200056//w k96cdisc/Figure 7.1007	Individual Plasma HIV-1 RNA (log10 copies/mL) Profiles by Visit – for CVF subjects (for Q4W arm)	The 1st vertical line indicates start of study treatment at Maintenance phase. The second vertical reference line indicates last IP on-treatment study day. i.e. min(last IP injection dose+35 days, LTFT HAART start date, date of last oral CAB+RPV+1). This vertical line is only for subjects who withdraw from Maintenance/Extension phase'	HL, WK48, 96, EOS

Efficacy: Figures					
No.	Population	IDSL / TST ID / Example Shell	Title	Programming Notes	Deliverable [Priority]
2.7.	ITT-E	Mid200056//wk96cdisc/Figure 7.1007	Individual Plasma HIV-1 RNA (log10 copies/mL) Profiles by Visit – for CVF subjects (for Current ART arm)	
The 1st vertical line indicates start of study treatment at Maintenance phase. The second vertical reference line indicates last on-treatment study day of Current ART. i.e. date of last Current ART dose; The third vertical reference line indicates last IP on-treatment study day. i.e. min(last IP injection dose+35 days, LTFT HAART start date, date of last oral CAB+RPV+1).
 
The 2nd vertical reference line is only for subjects who withdraw or completed Maintenance phase, the 3rd vertical reference line is only for those withdraw from Extension phase
	HL, WK48, 96, EOS

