13.14.2.1. Futility analysis

An interim analysis for the purpose of review by the IDMC will be performed.

A futility rule will assess the evidence that the CAB LA + RPV LA treatment arm is non-inferior to the control arm (CAR). This rule will use the interim data (50% completing Week 24) to calculate the Bayesian predictive probabilities that the CAB LA + RPV LA arm is non-inferior to the CAR arm. A 6% non-inferiority margin will be used for this study.

For this analysis of CAB LA + RPV LA snapshot 'HIV-1 RNA \geq 50' rate relative to CAR, let:

X_{CR}^I = number of snapshot 'HIV-1 RNA \geq 50' at interim in CAB LA + RPV LA arm,

N_{CR}^I = number of subjects on CAB LA + RPV LA arm at interim,

X_{CAR}^I = number of 'HIV-1 RNA \geq 50' at interim in Triumeq/current ART arm, and

N_{CAR}^I = number of subjects on Triumeq/current ART at interim.

Since the true response rate is unknown, prior distributions are placed on these parameters of interest to reflect current beliefs and balanced with acceptable decision criteria performance. Conjugate beta densities are assumed. Since we are anticipating rather large sample sizes at the interim, we simply chose Jeffrey's priors for the response rates (Beta(0.5,0.5)), leading to the posterior distributions on the response rates, based on the interim data:

$$P_{CR} \sim \text{Beta} (0.5 + X_{CR}^I, N_{CR}^I + 0.5 - X_{CR}^I),$$

$$P_{CAR} \sim \text{Beta} (0.5 + X_{CAR}^I, N_{CAR}^I + 0.5 - X_{CAR}^I).$$

The posterior predictive probability distribution of the final response data given the final sample sizes:

X_{CR}^F = number of snapshot 'HIV-1 RNA \geq 50' in the final dataset in CAB LA + RPV LA arm,

N_{CR}^F = number of subjects on CAB LA + RPV LA arm at the final analysis,

X_{CAR}^F = number of 'HIV-1 RNA \geq 50' in the final dataset in Triumeq/current ART arm

N_{CAR}^F = number of subjects on Triumeq/current ART arm at the final analysis.

The number of future observed 'HIV-1 RNA \geq 50' in each arm follows a beta-binomial distribution:

$$X_{CR}^F - X_{CR}^I | X_{CR}^I \sim \text{beta-binomial} (N_{CR}^F - N_{CR}^I, 0.5 + X_{CR}^I, 0.5 + N_{CR}^I - X_{CR}^I)$$

$$X_{CAR}^F - X_{CAR}^I | X_{CAR}^I \sim \text{beta-binomial} (N_{CAR}^F - N_{CAR}^I, 0.5 + X_{CAR}^I, 0.5 + N_{CAR}^I - X_{CAR}^I)$$

The posterior predictive probability (PPP) with a 6% for study individual study, is:

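### The by-visit error bars for HIV-1 RNA ≥50 c/mL switch from exact to normal-approximation limits as soon as one failure occurs, giving negative lower limits and an upper limit that falls when a failure is added

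*SAP*

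**What the plan says.** Note 4 to Table 4 (SAP section 7.2.5) describes the display: "Line plots, with 95% confidence intervals(CIs), for the proportion of subjects HIV-1 RNA ≥50c/mL for overall and by treatment group at each visit". It then fixes the interval method: "The 95% CIs will be calculated using Exact (Clopper-Pearson) confidence interval if the proportion is 0%. Otherwise, they are derived using the normal approximation". The note sets no truncation at zero and no minimum count for using the approximation.

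The display is Efficacy Figure 2.1 in section 13.13.6, titled "Proportion (95% CI) of Subjects with HIV-1 RNA" ≥50 c/mL by visit. It is scheduled for the headline and Week 48 deliveries.

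Three other statements bear on how the rule behaves:

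- Section 2.3 gives the size of the trial: "N=570, randomized 1:1 to each arm".
- Section 13.6.4 gives the denominator of the Snapshot rate: "Number of subjects in the analysis population". The denominator therefore does not shrink at later visits.
- Section 2.3 limits entry to suppressed participants: "Documented evidence of at least two plasma HIV-1 RNA measurements <50 c/mL in the 12 months prior to Screening". The plotted event should therefore be uncommon.

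**The concern.** Treating 0% as a special case concedes that the normal approximation fails for rare events. The rule then applies the approximation at one, two and three events, where it fails for the same reason. Two results are visible to any reader: a lower limit below zero for a proportion, and an upper limit that improves when a participant fails. A third is not visible: over part of the plausible range of rates the upper limit is too low, so the bars understate how high the failure rate could be. What is at stake is the reading of a headline figure on the primary endpoint measure. No decision rule depends on it.

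**Working it through.** **Inputs.** The confidence level is 95%, taken as two-sided (Table 4 note 4). There are 570 participants randomized 1:1, so 570/2 = 285 per arm, and 570 for the overall line (section 2.3). The ITT-E population could be slightly smaller. The true failure rate per visit is not in the SAP. It is an assumption here, examined from 0.5% to 4%.

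**A figure in the plan reproduced first.** The SAP prints no interval limits, so the nearest check is on the arm size. The Table 22 predictive probabilities (section 13.14.2.1) were recomputed with beta-binomial predictions, Jeffreys priors, 143 per arm at the interim and the margin stated there ("A 6% non-inferiority margin will be used for this study"). With 285 per arm at the end, six cells match the printed values: 17.3, 6.1, 30.6, 18.9, 13.3 and 93.9. With 286 the first cell becomes 17.0. So 285 is the arm size the plan itself uses.

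**Formulas for x failures out of n.**

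- x = 0, exact: lower limit 0, upper limit 1 − 0.025^(1/n).
- x ≥ 1, normal approximation: p ± 1.96·√(p(1−p)/n), with p = x/n.

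For n = 285 and x = 0, the upper limit is 1 − 0.025^(1/285) = 1.29%. For x = 1, p = 0.351% and the half-width is 1.96·√(0.00351·0.99649/285) = 0.69%, which gives −0.34% to 1.04%.

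| Failures of 285 | Rule as written | Clopper-Pearson | Wilson |
|---|---|---|---|
| 0 | 0 to 1.29% | 0 to 1.29% | 0 to 1.33% |
| 1 | −0.34 to 1.04% | 0.01 to 1.94% | 0.06 to 1.96% |
| 2 | −0.27 to 1.67% | 0.09 to 2.51% | 0.19 to 2.52% |
| 3 | −0.13 to 2.24% | 0.22 to 3.05% | 0.36 to 3.05% |
| 4 | 0.04 to 2.77% | 0.38 to 3.55% | 0.55 to 3.55% |
| 6 | 0.44 to 3.77% | 0.78 to 4.53% | 0.97 to 4.52% |

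**Negative lower limits.** The lower limit is below zero when x < 1.96²·(1 − x/n) = 3.84·(1 − x/n). At this arm size that means 1, 2 or 3 failures, and never 4 or more.

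**Falling upper limit.** For large n the exact upper limit at zero is about −ln(0.025)/n = 3.69/n. The approximate upper limit at one failure is about (1 + 1.96)/n = 2.96/n. The reversal is therefore built into the rule and does not depend on the arm size. On the overall line (n = 570) the upper limit goes from 0.65% to 0.52%. It occurs only between zero and one failure.

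**Coverage at n = 285, by enumerating the binomial distribution.**

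| Assumed true rate | Coverage, rule as written | Upper limit below truth | Chance of 1 to 3 failures |
|---|---|---|---|
| 0.5% | 99.9% | 0% | 70% |
| 1% | 99.7% | 0% | 62% |
| 1.25% | 89.6% | 10.0% | 49% |
| 1.5% | 92.4% | 7.2% | 37% |
| 2% | 92.0% | 7.5% | 17% |
| 2.5% | 92.1% | 7.3% | 7% |
| 3% | 92.5% | 6.9% | 3% |

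The nominal chance that the upper limit lies below the truth is 2.5%. Clopper-Pearson stays at or below 2.2% for these rates. Coverage of the plan's rule jumps because the counts are discrete; it is about 85% near a true rate of 1.05%.

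**The case against.** The strongest reply is that no inference rests on these bars. Table 4 lists the plots under Summary, not under Stats Analysis. The primary test uses the stratified CMH difference with the Sato variance (section 7.1.5.1), futility uses a predictive probability, and monitoring of confirmed virologic failure uses thresholds in the IDMC Charter. The Week 48 result also goes out at headline as Table 2.1. This stands, and it limits the point to a descriptive figure.

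A second reply is that the visible fault and the hidden one mostly occur at different true rates. Negative limits are most likely at 0.5% to 1%, where the rule does not under-cover. At 3% they are rare. The under-coverage elsewhere is modest, and Clopper-Pearson is itself conservative (about 96.5% to 97.9% at true rates of 1.5% to 4%). This also stands. It does not rescue the rule, because the falling upper limit and the negative limits need no assumption about the true rate once those counts occur. Software might clip bars at zero, but the SAP does not say so, and clipping would leave the reversal in place.

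A reader might carry the fault over to the subgroup differences, where a normal-approximation interval for no failures in either arm would have zero width. The SAP does not support that reading. Section 7.1.5.1 says only "Unadjusted difference in proportions between treatment groups and corresponding two-sided 95% CI will also be presented by subgroups" and names no method. Notes 6, 7 and 9 to Table 4, on the plots for <50, <200 and ≥200 c/mL and on the subgroup differences, name none either. Note 4 governs single proportions by visit at the ≥50 c/mL threshold.

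**Conclusion.** The rule is wrong as written for the note 4 plots. At 285 per arm it gives negative lower limits at 1 to 3 failures and an upper limit that falls from 1.29% to 1.04% when the first failure occurs (0.65% to 0.52% on the overall line). These results follow from the stated rule and the stated sample size, with normal approximation read as the usual Wald interval.

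The coverage result, about 90% to 92.5% with the upper limit too low 7% to 10% of the time, rests on assumed true rates of 1.25% to 3%, which the SAP neither gives nor excludes. At 0.5% to 1% there is no under-coverage. A reader might infer that the non-inferiority conclusion is at risk. It is not, because that conclusion does not use this interval. The point is a minor correction to a descriptive figure that is shown at headline.

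**What to change.** In Table 4 note 4, replace the two-part rule with one method, Clopper-Pearson or Wilson, applied at every visit and every count, for each arm and for the overall line. Either method keeps the lower limit at or above zero and makes the upper limit rise with each added failure.

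The cost is one sentence in the SAP, one program option and slightly wider intervals. At three failures, for example, the width goes from 2.24 + 0.13 = 2.37 percentage points to 3.05 − 0.22 = 2.83 with Clopper-Pearson. No new data are needed, and the primary analysis, the error rate and the sample size do not change.
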